5.3. Immunogenicity

[figure not shown]
5.3.1. Analysis of immunogenicity planned in the protocol

All immunogenicity analyses in stage A will be based on the Per Protocol - Immunogenicity set.

Note: In the immunogenicity sub-cohort, only those samples for which a pair (both maternal and respective infant) exist will be analyzed to evaluate secondary immunogenicity objectives and to assess antibody persistence in infants.

When performing experiments to monitor the stability of the RSV NEUT A assay overtime, a QC panel excursion was observed for tests performed after May 2023. Consequently, the testing was temporarily paused and not all samples were tested.

Secondary Immunogenicity Endpoints – Maternal Participants	Statistical Analysis Methods

Neutralizing antibody titers against RSV-A 
Measured on blood samples collected at Day 1 before vaccination (Visit 1), at Day 31 (Visit 2), and at delivery (Visit 3).
	

[figure not shown]
Secondary Immunogenicity Endpoints – Cord blood / placental transfer	Statistical Analysis Methods

 RSVPreF3 IgG-specific antibody concentration measured on blood samples collected at Delivery and cord blood* The ratio between cord blood* and maternal RSVPreF3 IgG-specific antibody concentrations 
* or an infant blood sample collected within 72 hours after birth (if no cord blood sample can be obtained).
	
CCI
 

Secondary Immunogenicity Endpoints – Infant Participants
	

 Neutralizing antibody titers against RSV-A. 
Measured on the cord blood sample collected at delivery (or on a blood sample collected from the infant within 72 hours after birth if no cord blood sample can be obtained) and at Day 43 (Visit 2-NB), Day 121 (Visit 3-NB), or Day 181 (Visit 4-NB) after delivery in 3 sub-cohorts of infants. Infants born to women in the immunogenicity sub-cohorts will be randomly assigned (1:1:1) to sample collection at 1 of the 3 timepoints noted.
	

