To evaluate the immunogenicity of the RSV Maternal vaccine in a sub-cohort of infants in Stage A, at birth and up to 6 months after birth.	
 
Neutralizing antibody titers against RSV-A
 
 Measured on the cord blood sample collected at delivery, or on a blood sample collected from the infant within 72 hours after birth (if no cord blood sample can be obtained).  Measured on a blood sample collected at Day 43 (Visit 2-NB), Day 121 (Visit 3-NB), or Day 181 (Visit 4-NB) after birth in 3 sub-cohorts of infants.  Infants born to women in the immunogenicity sub-cohort will be randomly assigned (1:1:1) to sample collection at 1 of the 3 timepoints noted.
To evaluate the transfer of RSV-specific antibodies from a sub-cohort of maternal participants vaccinated with a single IM dose of the RSV Maternal vaccine to their infants at the time of delivery.	
RSVPreF3 IgG-specific antibody concentration measured on blood samples collected at Delivery and cord blood*
 The ratio between cord blood* and maternal RSVPreF3 IgG-specific antibody concentrations.  * or an infant blood sample collected within 72 hours after birth (if no cord blood sample can be obtained).
Secondary safety objectives	Secondary safety endpoints
To evaluate reactogenicity of a single IM dose of the RSV Maternal vaccine in stage A maternal participants, during a 7 day follow up period after the study intervention.	Occurrence of solicited administration site and systemic events in stage A maternal participants, during a 7-day follow-up period after the study intervention (i.e. the day of the intervention and 6 subsequent days).
To evaluate the safety of a single IM dose of the RSV Maternal vaccine in all maternal participants, during a 30 day follow up period after the study intervention.	Occurrence of unsolicited adverse events (AEs) in all maternal participants during a 30-day follow-up period after the study intervention (i.e. the day of the intervention and 29 subsequent days).

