**Table 5 Study groups, sub-cohorts, interventions, and blinding foreseen in the study: Stage A**

Approximately 4600 maternal participants will be randomized during Stage A.

Study groups	Maternal participants (M)				Infant participants (I)			Study Groups for Randomization  (Allocation 12:2:2:2:6:1:1:1)	Blinding		
	~Number	Age in Years (Min/Max)	Intervention name	Maternal Blood Sampling Sub-cohorts		Infant Blood Sampling sub-cohorts			M only	M + I	I only
				Name	~Number	Name	~Number		Screen-ing	Up to D181 post delivery/ birth	D271, D366 post delivery/ birth
									-	Double blind	Double blind
RSV_MAT	~3067	18-49	RSV_MAT	RSV_MAT_0	~2040	RSV_MAT_0	~2040	RSVMAT_0	•	•	•
		18-49	RSV_MAT	RSV_MAT_I	~1020	RSV_MAT_BS1	~340	RSVMAT_BS1		•	
						RSV_MAT_BS2	~340	RSVMAT_BS2		•	
						RSV_MAT_BS3	~340	RSVMAT_BS3		•	
Control	~1533	18-49	Control	Control_0	~1020	Control_0	~1020	Control_0	•	•	•
		18-49	Control	Control_I	~510	Control_BS1	~170	Control_BS1		•	
						Control_BS2	~170	Control_BS2		•	
						Control_BS3	~170	Control_BS3		•	

Control = Placebo; Infant sub-cohorts are abbreviated “BS1;” “BS2;” BS3” and correspond to visits 2-NB (Day 43), 3-NB (Day 121) and 4-NB (Day 181), respectively.

RSVMAT\_0 and Control\_0 = maternal and infant participants who are not in a sub-cohort for immune response assessment.

RSVMAT\_I and Control\_I = maternal sub-cohorts for immune response assessment.

RSVMAT\_BS1, \_BS2, \_BS3 = infants born to women in the RSVMAT\_I sub-cohort and evaluated for immune response at the designated timepoint (D43, D121 or D181).

Control\_BS1, \_BS2, \_BS3 = infants born to women in the Control\_I sub-cohort evaluated for immune response at the designated timepoint (D43, D121 or D181).

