**Randomization to the immunogenicity subcohort:**

When they are randomized to a study intervention, maternal participants in Stage A (as well as their as yet unborn infants) will *also* be randomized either to participate in the immunogenicity sub-cohort (N ~ 1533) or to not participate (N ~ 3067).

For the ~ 1533 maternal participants in the immunogenicity sub-cohort, an additional blood sample will be collected at delivery.

For the ~ 1533 infant participants in the immunogenicity sub-cohort:

[figure not shown]
- Randomization will identify a single timepoint post-birth (Day 43 (Visit 2-NB), or Day 121 (Visit 3-NB), or Day 181 (Visit 4-NB)) at which each (as yet unborn) infant will have a blood sample collected. Thus, at each of the 3 post-birth immunogenicity timepoints, a sample will be collected from approximately one third of the infants in the sub-cohort (N ~510).

Note that due to the stop on study enrollment and vaccination, there will no longer be collection of blood samples from the infants at V2-NB, V3-NB and V4-NB.

***Note: In the immunogenicity sub-cohort, only those samples for which a pair (both maternal and respective infant) exist will be analyzed to evaluate secondary immunogenicity objectives and to assess antibody persistence in infants.***

Refer to [Figure 4](#) and [Table 5](#) for additional information.

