#### **10.6.4. Argentina**

*Concerning the “STUDY POPULATION – Exclusion criteria for enrolment – maternal participants” and, as per request from the Argentinean regulatory authorities (A.N.M.A.T - Administración Nacional de Alimentos, Medicamentos y Tecnología Médica), study recruitment in Argentina was limited to pregnant women aged 18 to 40 years (inclusive), instead of 18 to 49 years (inclusive).*

*This age limitation was initially expected to be temporal, and dependent on the availability of safety data coming from other countries on pregnant women > 40 years old, which was to be submitted to A.N.M.A.T for evaluation. However, further enrollment and vaccination in the study was stopped on 25th February 2022, before such safety data was submitted.*

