1. DOCUMENT HISTORY

Date	Description	Protocol Version
02 Nov 2020	Final	Amendment 1: 05 Oct 2020
01 Nov 2021	Amendment 1	Amendment 2: 23 Jun 2021
17 Nov.2022	Amendment 2	Amendment 4: 15 Mar 2022
03 Jan 2023	Amendment 3	Amendment 4: 15 Mar 2022
09 Mar 2023	Amendment 4	Amendment 5: 23 Feb 2023
21 Sep 2023	Amendment 5	Amendment 5: 23 Feb 2023

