- Randomized intervention allocation: A minimum of 4600 and up to a maximum of 10,000 pregnant women (maternal participants) will be randomly assigned (2:1) to receive the investigational vaccine or control (placebo) at Visit 1. Randomization will take place in 2 sequential stages, A and B. Approximately 4,600 maternal participants will be randomized into Stage A. Stage B will only start after the last participant is randomized in Stage A. Participants in stage A will be randomized (12:2:2:2:6:1:1:1 ratio) to be in the RSV group, in one of the 3 infant blood sampling sub-cohorts and receiving the investigational vaccine (RSVMAT_BS1 (Day 43), RSVMAT_BS2 (Day 121), RSVMAT_BS3 (Day 181)), in the Control group, or in one of the 3 infant blood sampling sub-cohorts receiving placebo (Control_BS1 (Day 43), Control_BS2 (Day 121), Control_BS3 (Day 181)). Randomization will be via the automated internet-based system (SBIR). The system's randomisation algorithm of maternal enrolment will use a minimisation procedure accounting for maternal age at the time of the study intervention (18-34, 35-39, ≥ 40 years of age), gestational age at the time of the study intervention ($24^{0/7}$ - $28^{0/7}$; $28^{1/7}$ - $34^{0/7}$), and center. Minimisation factors will have equal weight in the minimisation algorithm.
- Study (intervention) groups are described in [Table 2](#) and [Table 3](#)
- Data collection: standardized Electronic Case Report Form (eCRF). E-Diaries will be used to collect solicited event data.

- Safety monitoring will be conducted by an unblinded Independent Data Monitoring Committee (IDMC) and by an unblinded Safety Review Team*. The analyses for IDMC safety evaluations will be described in a separate SAP for IDMC.

** Due to the safety signal observed, the study was fully unblinded to ensure the safety of the participants.*

CONFIDENTIAL

212171 (RSV MAT-009)
Statistical Analysis Plan Amendment 5

Table 2 Study groups, sub-cohorts, interventions, and blinding foreseen in the study: Stage A

Approximately 4,600 maternal participants will be randomized during Stage A.

Study groups	Maternal participants (M)				Infant participants (I)			Study Groups for Randomization	Blinding			
	~Number	Age in Years (Min/Max)	Intervention name	Maternal Blood Sampling Sub-cohorts	Infant Blood Sampling sub-cohorts	(Allocation 12:2:2:2:6:1:1:1)	Screening		M only	M + I	I only	
				Name	~Number	Name	~Number					

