2050.Vx*	Intercurrent medical conditions which are exclusionary as per protocol	All
2060.Vx#+* 2060.Vx+*	Concomitant infection related to the vaccine which may influence immune response	All
2070.Vx#+* 2070.Vx+*	Concomitant infection not related to the vaccine but may influence immune response	All
2090.Vx	Participants did not comply with blood sample schedule 
 • For PPS at Visit 1/Day 1 check the interval of day 1 BS -0/+3 days; • For PPS at Visit 2/Day 43 post-birth, check the interval of day 43 BS -12/+18 days; • For PPS at Visit 3/Day 121 post-birth, check the interval of day 121 BS -10/+20 days; • For PPS at Visit 4/Day 181 post-birth, check the interval of day 181 -15/+20 days 	Visit 1-NB/Birth Visit 2-NB/Day 43 post-birth ^a Visit 3-NB/Day 121 post-birth ^a Visit 4-NB/Day 181 post-birth ^a
2100.Vx	Serological results not available (immunogenicity sample collected but invalid/no result)	Visit 1-NB/Birth Visit 2-NB/Day 43 post-birth ^a Visit 3-NB/Day 121 post-birth ^a Visit 4-NB/Day 181 post-birth ^a
2120.Vx	Obvious incoherence or abnormality or error in the data	Visit 1-NB/Birth Visit 2-NB/Day 43 post-birth ^a Visit 3-NB/Day 121 post-birth ^a Visit 4-NB/Day 181 post-birth ^a
2130.Vx	Testing performed on serology samples not aligned with ICF	Visit 1-NB/Birth Visit 2-NB/Day 43 post-birth ^a Visit 3-NB/Day 121 post-birth ^a Visit 4-NB/Day 181 post-birth ^a
2110.Vx	Immunogenicity sample collected but GSK decided not to test	Visit 1-NB/Birth Visit 2-NB/Day 43 post-birth ^a Visit 3-NB/Day 121 post-birth ^a Visit 4-NB/Day 181 post-birth ^a
3100	Birth is less than 4 weeks post-vaccination.	All

* Attribution of these elimination codes to participant need CRDL review of individual listing

Carry forward elimination from mother to infant

Vx+ indicates participants whose immunogenicity data will be eliminated from a specific visit onwards;

Vx indicates participants whose immunogenicity data will be eliminated from a specific visit.

^a As per Protocol Amendment 4, infant blood samples will not be collected at V2-NB, V3-NB and V4-NB. 2090.Vx, 2100.Vx, 2120.Vx, 2130.Vx will not be applicable to infant participants whose blood samples are not collected under Protocol Amendment 4.

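### Ending infant bleeds at Days 43, 121 and 181 on one calendar stop leaves the three randomised sub-cohorts covering different birth periods, so a reading of antibody persistence across them needs a common-birth-window check.

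*SAP*

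**What the plan says.** Protocol Table 4 sets the design of the infant endpoint: "Infants born to women in the immunogenicity sub-cohort will be randomly assigned (1:1:1) to sample collection at 1 of the 3 timepoints noted". Protocol 6.3.2.1.1 plans about 510 infants at each time-point, one bleed per infant.

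The bleeds were then withdrawn at all three visits at once. A footnote to SAP Table 8 (section 4.2.5.2) states: "As per Protocol Amendment 4, infant blood samples will not be collected at V2-NB, V3-NB and V4-NB". The SAP document history dates that version as "Amendment 4: 15 Mar 2022". Protocol 10.6.4 records that "further enrollment and vaccination in the study was stopped on 25th February 2022".

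SAP 5.3.1 limits testing to mother–infant pairs that have samples, and says that these "will be analyzed to evaluate secondary immunogenicity objectives and to assess antibody persistence in infants". It still describes the infants as assigned 1:1:1. The only immunogenicity sensitivity analysis named in SAP 5.3.2.1 excludes Bangladesh. SAP 9.2 does not replace missing measurements. The model for adjusted ratios in SAP 10.1.4.3 has group and country terms but nothing for birth date. SAP section 8 does not mention the matter.

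**The concern.** Because each infant gives one post-birth sample, change from Day 43 to Day 181 is seen only by comparing different infants. Randomisation to time-point made that comparison fair. A stop tied to the calendar rather than to infant age undoes part of it: an infant born shortly before the stop could reach Day 43 but not Day 121 or Day 181. The Day 181 group then holds only earlier births, while the Day 43 group holds earlier and later ones.

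If maternal or cord titres, country mix, gestational age at dosing or RSV exposure moved during enrolment, the movement would look like faster or slower antibody decay. The loss would also be hard to see in the output. The SAP Table 8 footnote makes codes 2090, 2100, 2120 and 2130 inapplicable to infants who were not bled under Amendment 4, so the elimination summary would not display it.

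**Working it through.** **Inputs.** Stage A size: "Approximately 4600 maternal participants will be randomized during Stage A" (Protocol Table 5). Allocation: "12:2:2:2:6:1:1:1 ratio" (SAP section 3), summing to 27. Total vaccinated: 5328 (Protocol 9.2). Stage B starts only after Stage A is full (Protocol 6.3.2.1.2). Nominal visit offsets are 42, 120 and 180 days after birth; allowed offsets are 30–60, 110–140 and 165–200 (Protocol Table 3, SAP Table 8).

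**Step 1: the plan's own figure.** Infants per time-point = 4600 × 3/27 = 511.1 (stated about 510), made up of 4600 × 2/27 = 340.7 vaccine (about 340) and 4600 × 1/27 = 170.4 control (about 170). Sub-cohort = 4600 × 9/27 = 1533.3 (about 1533). All reproduce.

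**Step 2: last usable birth = stop date − visit offset**, with the stop at 15 March 2022.

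| Bleed | Nominal day | Earliest allowed day | Latest allowed day |
|---|---|---|---|
| Day 43 | 1 Feb 2022 | 13 Feb 2022 | 14 Jan 2022 |
| Day 121 | 15 Nov 2021 | 25 Nov 2021 | 26 Oct 2021 |
| Day 181 | 16 Sep 2021 | 1 Oct 2021 | 27 Aug 2021 |

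The nominal gap between the first and last rows is 180 − 42 = 138 days. It does not depend on the stop date, provided a site stopped all three bleeds together.

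**Step 3: were there Stage A births in that gap?** Women beyond Stage A = 5328 − 4600 = 728. With enrolment ending on 25 February 2022, Stage A filled 728/325 = 2.2 months earlier (about 18 December 2021) or 728/400 = 1.8 months earlier (about 31 December 2021). Both rates are planning scenarios from the protocol's list of tables, not observed accrual. Stage A births therefore continued well past mid-September 2021.

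**Step 4: how many?** This was simulated under assumptions: even accrual ending 25 February 2022, gestational age uniform over 24–34 weeks at dosing and normal with mean 39.2 and SD 1.6 weeks at birth, every eligible infant bled on the nominal day, stop at 15 March 2022.

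| Accrual | Samples at Day 43 / 121 / 181 (511 planned each) | Day 43 infants born after the Day 181 cut-off | Median birth date, Day 43 vs Day 181 |
|---|---|---|---|
| 325/month | 477 / 386 / 315 | 34% | 13 Jul vs 5 May 2021 |
| 400/month | 452 / 339 / 251 | 45% | 30 Aug vs 22 Jun 2021 |

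With starts from November 2020 to March 2021, even or rising accrual, and stops from 25 February to 15 June 2022, the share was 19% to 80%. At 325/month with a 15 June 2022 stop it was 17%. It was never zero.

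**Step 5: what could this do to apparent decay?** Suppose late births differ from early births by 20% in titre. This is an assumption. The Day 43 GMT shifts by 1.2^0.34 = 1.06 to 1.2^0.45 = 1.09, that is, 6% to 9%. A true 40-day half-life means 138/40 = 3.45 halvings over 138 days. The shift is 0.34 × log2(1.2) = 0.09 to 0.45 × log2(1.2) = 0.12 halvings. At the larger value the apparent half-life is 138/(3.45 + 0.12) = 38.7 or 138/(3.45 − 0.12) = 41.4 days, so about 39 to 41.

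**The case against.** The readable plan specifies no slope, half-life or test across time-points. The endpoint is a titre at each time-point, SAP 9.2 describes results per assay and time-point, and SAP section 6 calls the comparative analyses descriptive and asks for caution. The infant methods cell in SAP 5.3.1 and all of 5.3.2.2 are redacted, so an adjustment may exist. All of this stands. A reader might infer that the SAP plans an invalid decay estimate, or that the sponsor ignored the problem; the documents support neither. What remains is that the samples' declared use is persistence, and that a row of GMTs at three ages will be read that way.

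The plan also has partial safeguards. SAP 5.1.1 summarises infant characteristics by immunogenicity sub-cohort, confirmed RSV infection can lead to per-protocol exclusion (Protocol 9.3.1.1.3), and each pair has a cord or birth sample. These could show or reduce an imbalance, but none aligns the birth periods.

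Nothing in the documents shows that titres drifted with birth date. Protocol 2.3 reports that the preterm-birth imbalance in low and middle-income countries peaked from August to December 2021; that shows that calendar period was not neutral for one outcome, and says nothing about antibody. Protocol 8.4.2.2.1 allows that pandemic measures may alter RSV seasonality, which makes drift plausible, not established.

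**Conclusion.** The point holds for comparison across time-points. The 138-day gap follows from the documents' own visit days and the common stop. The number of infants affected rests on assumed accrual, because first enrolment, the accrual curve, site-level stop dates and numbers bled are not given.

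Three stronger readings should be resisted. First, a reader might carry a 20% early-to-late titre difference straight into a 20% error in the Day 43 to Day 181 fall. Late births are only about a third to under half of the Day 43 group in the two planning-rate scenarios, so the shift there is about 6% to 9%. Second, a reader might extend the concern to vaccine versus control. Within one time-point the calendar cut falls on both arms, so that comparison is broadly protected. Third, a reader might take all infant sampling to have ended; birth samples taken when cord blood was missing are not covered by the stop.

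The likely bias is therefore modest, but from the readable plan it cannot be checked.

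**What to change.** In SAP 5.3.2.1, add a sensitivity analysis that repeats the RSV-A GMTs at cord/birth, Day 43, Day 121 and Day 181, by arm, in infants born early enough to have been eligible for all three bleeds. Set the last birth date by country or site from the implementation of Amendment 4. Also report, by arm and time-point, the within-infant geometric mean ratio of the post-birth titre to that infant's own cord or birth titre, where both results exist. Tabulate numbers bled and the birth-date distribution by sub-cohort. If the redacted text already does this, a cross-reference is enough.

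The cost is programming only, with no new sampling or testing. The restricted check has fewer Day 43 and Day 121 infants: in the scenarios above, about 315 or 251 per time-point. The ratio analysis loses pairs with an untested sample, since SAP 5.3.1 reports that RSV-A neutralisation testing was paused after a quality-control excursion and not every sample was tested.

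The limits should be stated with the results. The common window removes the calendar cut, but not losses from untested samples or visit-specific per-protocol exclusions, so it does not fully restore the randomised comparison. The ratio removes differences in starting titre, but not in decay or later RSV exposure.

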5.3.2. Additional considerations

[figure not shown]
5.3.2.1. Sensitivity analysis

A sensitivity analysis will be performed based on the Per Protocol-Immunogenicity set excluding participants in Bangladesh.

5.3.2.2. Between group analysis

CCI

5.4. Analysis of safety and reactogenicity

5.4.1. Analysis of safety and reactogenicity planned in the protocol

Safety analyses in **maternal participants** will include summaries by study group and age category (18-34, 35-39, ≥ 40 years of age; overall) of solicited administration site and systemic events (for stage A subjects), unsolicited AEs, MAEs, SAEs, MA-RTIs (RSV-associated MA-RTIs and all-cause MA-RTIs), AEs leading to study withdrawal, pregnancy outcomes and pregnancy related AESIs.

Safety analyses in **infant participants** will include summaries by study group, overall and gestational age at birth (≥ 37 weeks or < 37 weeks) of neonatal AESIs, MAEs, SAEs, AEs leading to study withdrawal, and the occurrence of RSV-associated RTIs, LRTIs, severe LRTIs, RSV-associated hospitalizations, all-cause RTI and all-cause LRTI.

Safety analyses for maternal participants and infants may also be reported by economic region (LMIC and HIC).

Analyses of solicited AEs will be performed on the Solicited Safety set (maternal participants only). Analyses of unsolicited AEs will be performed on the ES.

Primary Safety Endpoints – Infant Participants	Statistical Analysis Methods

Occurrence of SAEs, AEs leading to study termination and medically attended AEs from birth up to 6 months after birth
 
Occurrence of SAEs, AEs leading to study termination and medically attended AEs from birth up to 12 months after birth.
	
CCI

Secondary Safety Endpoints – Maternal Participants	Statistical Analysis Methods

Occurrence of solicited injection site and systemic events in Stage A participants during a 7-day follow-up period after vaccination (i.e. the day of vaccination and 6 subsequent days).
	
CCI

Occurrence of unsolicited adverse events (AEs) in all maternal participants during a 30-day follow-up period after vaccination (i.e. the day of vaccination and 29 subsequent days).
	

	CCI

Pregnancy outcomes from Day 1 (Visit 1) up to 6 weeks after delivery (Day 43 post-delivery, Visit 4). These include live birth with no congenital anomalies, live birth with minor congenital anomaly(ies) only; live birth with at least one major congenital anomaly, fetal death/still birth (antepartum or intrapartum) with no congenital anomalies, fetal death/still birth (antepartum or intrapartum) with minor congenital anomalies only, fetal death/still birth (antepartum or intrapartum) with at least 1 major congenital anomaly; elective/therapeutic termination with no congenital anomalies; elective/therapeutic termination with minor congenital anomalies only, and elective/therapeutic termination with at least 1 major congenital anomaly.
	

Pregnancy-related adverse events (AEs) of special interest from Day 1 (Visit 1) up to 6 weeks after delivery (Day 43 post-delivery, Visit 4). These include maternal death, hypertensive disorders of pregnancy (gestational hypertension, pre-eclampsia, pre-eclampsia with severe features including eclampsia), fetal growth restriction, pathways to preterm birth (premature preterm rupture of membranes, preterm labor, provider-initiated preterm birth), gestational diabetes mellitus, chorioamnionitis.
	

Occurrence of serious adverse events (SAEs), AEs leading to study termination, and medically attended AEs in all maternal participants from Visit 1 (Day 1) up to 6 months after delivery.
	

Secondary Safety Endpoints – Infant Participants
	

The occurrence of neonatal AEs of special interest (reported up to 6 weeks after birth). These include small for gestational age, low birth weight including very low and extremely low birth weight (<2500 g, <1500g, <1000g), congenital anomalies (major external structural defects, internal structural defects, functional defects), neonatal death (in an extremely pre-term birth ($22 \leq GA < 28$ weeks), in a preterm live birth ($28 \leq GA < 37$ weeks), or in a term live birth), preterm birth.
	

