All safety data will be reviewed by a blinded Safety Review Team (SRT)\* and an unblinded Independent Data Monitoring Committee (IDMC) on an on-going basis.

A firewall will be established to ensure that data are not inadvertently unblinded. Details are provided in a separate Firewall charter.

*\* Due to the safety signal observed, the study was fully unblinded to ensure the safety of the participants.*

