#### **6.3.6. Blinding and unblinding**

To minimize the introduction of bias, this study will be double-blinded\*. Participants will not have access to their randomization assignment, and investigators and their staff will be blinded to the participant's assigned study intervention throughout the course of the study.

The laboratory in charge of the sample testing will be blinded to the intervention assignment. Codes will be used to link the participant and study (without any link to the intervention attributed to the participant) to each sample.

A firewall will be established to ensure that data are not inadvertently unblinded. Details are provided in a separate Firewall charter.

*\* Following the decision to stop enrollment and vaccination, the study/site staff and maternal participants no longer stay blinded. Refer to Section 2.3 for details.*

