8. CHANGES FROM PLANNED ANALYSES

- By-participant listings of SAEs, AEs leading to study withdrawal, MAEs, adverse pregnancy outcomes and pregnancy related AESIs will be prepared and released. Such listings have already been released in earlier analyses. Due to study enrolment/vaccination stop, the study has been unblinded already before the final analysis.
- A sensitivity analysis for immunogenicity results excluding participants from Bangladesh, for which HIV testing was not performed before their enrollment into the study, has been added.
- Between group evaluations for immunogenicity analysis was clarified to be performed among RSV MAT and Control instead of vaccination groups, the wording has been corrected.
- In February 2022, enrollment and vaccination were stopped because of an imbalance in preterm births and associated neonatal deaths observed between the RSVPreF3-Mat and placebo groups. Subsequently the study was unblinded, and therefore the presented VE endpoints are descriptive.
- Subgroup analyses by economic region (LMIC and HIC) will be performed for demography, efficacy, and safety evaluations.
- Subgroup analyses by gestational age at birth will be performed for demography and safety evaluations.
- Sensitivity analysis for primary efficacy endpoints by using a negative binominal regression model have been removed.

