10.1.2.10. Onset day

The onset day for an event (e.g. AE, medication, vaccination) is the number of days between study vaccination and the start date of the event. This is 1 for an event occurring on the same day as vaccination (and reported as starting after vaccination).

The onset day for an event (e.g. neonatal AEs, SAEs, AEs of special interest) for infants is the number of days between birth and the start date of the event (or date of diagnosis). This is 1 for an event occurring on the same day as birth.

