10.2. TFL TOC

The Table Figure Listing (TFL) TOC which itemizes the planned list of TFL and their associated lay-out is developed as a separate document. There will be one TOC document for the interim analysis of Day43PD and another for the 6-month PD interim analysis and the final analysis.

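### The primary infant safety analysis combines follow-up from before and after unblinding, and the readable SAP text plans no by-arm comparison within each period

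*SAP*

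**What the plan says.** The primary infant safety endpoints are SAEs, MAEs and AEs leading to study termination, from birth to 6 months and from birth to 12 months (Protocol Table 4; SAP 5.4.1). Protocol 9.4.3 places them on the Exposed set. SAP 7.1 schedules the final safety analysis for all participants once every infant has completed month 12.

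The readable breakdown for infants is that analyses "will include summaries by study group, overall and gestational age at birth"; economic region is optional. The methods cells are redacted, and SAP 10.2 adds: "The Table Figure Listing (TFL) TOC which itemizes the planned list of TFL and their associated lay-out is developed as a separate document".

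On unblinding, Protocol 6.3.6 states: "Following the decision to stop enrollment and vaccination, the study/site staff and maternal participants no longer stay blinded". Protocol 1.2 states: "Due to the safety signal observed, the study was fully unblinded to ensure the safety of the participants". The stop is dated in Protocol 10.6.4: "further enrollment and vaccination in the study was stopped on 25th February 2022". The unblinding date itself is not given.

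SAP 8 deals with unblinding in two places. For efficacy: "Subsequently the study was unblinded, and therefore the presented VE endpoints are descriptive". For safety: "By-participant listings of SAEs, AEs leading to study withdrawal, MAEs, adverse pregnancy outcomes and pregnancy related AESIs will be prepared and released". The footnote to SAP Table 6 adds that the elimination code for a broken randomisation code does not apply to the study-wide unblinding.

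**The concern.** Protocol 10.3.9.3 defines medical attention as a hospital stay or any unscheduled contact with medical personnel. Whether an infant has an MAE therefore depends partly on a parent's decision to seek care. After the stop, parents and staff made such decisions knowing the allocation, and a preterm-birth signal had been identified. Two routes into the data also depend on judgement: the Day 8 contact, made if the investigator or parent thinks it necessary (Protocol Table 2), and the RTI assessment visit, which a parent's intention to seek care can trigger (Protocol 8.4.3.2).

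If MAE detection changed differently in the two arms, the pooled comparison of a primary endpoint would mix a blinded and an unblinded component, and a reader could not separate them. The SAP draws a consequence of unblinding for vaccine efficacy but none, in readable text, for this endpoint.

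**Working it through.** The plan gives no figure to reproduce. The check has two parts.

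**1. Is a split planned in readable text?** SAP 5.4.1 gives group, overall, gestational age at birth and optional economic region. SAP 8 adds subgroups by economic region and gestational age, and listings. SAP 7.1 describes monthly and ad hoc safety analyses without specifying a split. None of these is by blinding period.

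**2. How much follow-up is unblinded, and could it matter?**

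Inputs from the documents:
- 5235 infants, 3496 active, hence 5235 − 3496 = 1739 control (Protocol 2.3).
- 5328 women vaccinated (Protocol 9.2); stop on 25 Feb 2022 (Protocol 10.6.4).
- Accrual of 400 or 325 per month (operating-characteristics titles in the Protocol's list of tables): 5328/400 = 13.3 and 5328/325 = 16.4 months. The protocol date of 26 Jun 2020 bounds accrual at 20 months.

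Assumptions, because the documents do not give them:
- unblinding on 25 Feb, 15 Mar (date of Amendment 4), 30 Apr or 30 Jun 2022;
- accrual uniform, or rising linearly up to the stop;
- gestational age at vaccination uniform over 24 to 34 weeks, delivery at 39 weeks, no dropout;
- 30%, 50% or 70% of infants with an MAE by 12 months, at a constant rate;
- MAE detection in one arm changed by δ = 5%, 10%, 15% or 20% after unblinding.

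Four dates, three accrual durations and three MAE proportions give 36 scenarios for each accrual shape.

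*Unblinded share of 0 to 12 month person-time.* Uniform accrual, for 13.3, 16.4 and 20 months:
- 25 Feb: 62, 51, 41%
- 15 Mar: 58, 47, 39%
- 30 Apr: 47, 38, 31%
- 30 Jun: 33, 26, 22%

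Rising accrual gives 36% to 79%. A separate simulation (uniform accrual, delivery at 40 weeks, unblinding up to 15 Jun) gives 25% to 63% of 12-month and 10% to 41% of 6-month follow-up. Both periods are present in every scenario.

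*Pooled 95% margin for a null ratio of proportions:* exp(1.96 × √[(1−p)/p × (1/3496 + 1/1739)]) − 1. For p = 0.5 this is exp(1.96 × 0.02934) − 1 = 5.9%. For p = 0.3 it is 9.2% and for p = 0.7 it is 3.8%.

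*Shift in the null ratio:* for an infant with unblinded fraction f, the MAE probability is 1 − exp[−λ(1 + fδ)] with λ = −ln(1 − p). This is averaged over infants and divided by p. Example: 15 Mar, 16.4 months, p = 0.5. With δ = 20% the average is 0.531, a shift of 6.2%, just above the 5.9% margin. With δ = 10% it is 0.516, a shift of 3.2%, well below.

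Scenarios out of 36 in which the shift exceeds the margin:

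| δ | Uniform accrual | Rising accrual |
|---|---|---|
| 5% | 0 | 0 |
| 10% | 0 | 1 |
| 15% | 3 | about 15 |
| 20% | 13 | 29 |

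The 15% count under rising accrual is 15 or 16, because one scenario lies almost on the margin (shift 9.19% against 9.18%). Shifts under uniform accrual are 1.1% to 5.1% at δ = 10% and 2.1% to 10.0% at δ = 20%. The scenarios carry no weights, so the counts are not probabilities.

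**The case against.** The strongest objection is that absence cannot be shown: the methods cells are redacted and the table list is not available. A reader might infer that the plan has no such analysis. The documents do not support that, and the point is limited to the readable text. The sponsor can close it by citing an existing table.

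A reader might also infer that the infant safety result is biased. That is not supported either. The documents contain no evidence of differential detection, and the excess over the margin almost disappears at δ = 10%. Protocol Table 2 has SAEs and MAEs collected at every visit and surveillance contact in both arms, which limits the scope for bias.

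Nor does the point touch the preterm-birth finding. The IDMC saw that imbalance in February 2022 (Protocol 2.3), and site staff and mothers were unblinded only after the decision to stop (Protocol 6.3.6).

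The care-seeking argument belongs to MAEs. No comparable mechanism is shown for deaths or life-threatening SAEs, so SAEs should not be called equally susceptible.

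It can also be said that the listings and continuing safety reviews suffice. The listings would allow a reconstruction, with some work: onset day "for infants is the number of days between birth and the start date of the event", so birth and unblinding dates are needed as well. Listings still give no person-time and no comparison by arm. The monthly and ad hoc analyses in SAP 7.1 are not described as doing this.

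**Conclusion.** The point holds as an optional improvement. It is well supported that the 12-month window mixes blinded and unblinded follow-up: the unblinded share is about 22% to 79% across all assumed dates and accrual patterns. Material bias is not shown. It depends on a differential detection change for which the documents give no value: none of the scenarios exceeds the margin at 5%, at most one at 10%, and 13 or 29 of 36 at 20%. Its direction is unknown. These results rest on the assumed unblinding date, accrual pattern and MAE proportions.

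A comparison restricted to the blinded period would be less exposed to unblinding-related detection bias. It would not be free of it, because an event that started before unblinding may have been reported at a later, unblinded contact.

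**What to change.** Record the unblinding date, by site if it differed. In SAP 5.4.1, for the final analysis, add a supplementary table of infant MAEs by arm, split by whether the event's calendar start date falls before or after unblinding, with person-time. Compare arms within each period. Use the recorded start date; if it is rebuilt from onset day, the formula is birth date plus onset day minus 1, because SAP 10.1.2.10 sets onset day to 1 on the day of birth.

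- SAEs may be shown alongside for completeness.
- Where report dates are held, add a version limited to events that both started and were reported before unblinding.
- Tabulate Day 8 contacts by arm only for the period after Amendment 4, which introduced them.
- State that Amendment 4 also added monitoring contacts, and that the periods differ in infant age and season, so the periods should not be compared with each other.
- Label the table post hoc and descriptive, and keep the pooled Exposed set summary as the main result.

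The cost is one date variable and a few tables. New collection is unlikely to be needed. A woman vaccinated on 25 Feb 2022 at 24 weeks and delivering at 40 weeks gives birth 112 days later, on 17 Jun 2022; the 400-day limit for the last infant visit then ends on 22 Jul 2023, before the SAP date of 21 Sep 2023. The downside is precision: with uniform accrual, the 95% margin of the MAE ratio is about 5% to 16% before unblinding and 6% to 22% after it, against 4% to 9% pooled.
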